2. STUDY PROCEDURES

a. Procedures

Hemodialysis patients with sufficient residual native kidney function will undergo two 4-week study periods in a cross-over design. During these periods, hemodialysis will be prescribed three times per week and two times per week according to a formula put forward by a National Kidney Foundation Committee.

Screening:

- local nephrologists will be contacted to identify patients with measured residual kidney function or patients who report still producing urine.
- informed consent will be obtained from eligible patients.
- patients who consent will then undergo a run-in period followed by randomization into the cross-over study if they have adequate residual function.

Run-in period:

- patients' residual kidney function (Kru) will be measured by urine and blood collection.
- if Kru is >2.5 ml/min, patients will then proceed into the crossover study periods after completing the following steps:
 - receive extra dietary counseling in addition to routine dietary advice provided by the dialysis unit
 - diuretic doses will be optimized

Cross-over study with two 4-week study periods.

During each period:

- hemodialysis will be prescribed to achieve adequate treatment according to current National Kidney Foundation Committee guidelines.
- patients will be visited weekly.
- patients will continue to obtain blood work monitoring as per their routine dialysis care.
- hemodialysis and medications will be adjusted by the patients' primary nephrologist as needed.
- receive extra dietary counseling in addition to routine dietary advice provided by the dialysis unit

At the end of each 4-week period:

- patients' residual kidney function will be measured.
- pre- and post-treatment blood samples will be collected at the last treatment of the period. Blood will be collected through the dialysis tubing in the same fashion as the patients' routine lab monitoring.
- waste dialysate, which normally gets thrown away, will be collected during the last treatment.
- patients will complete symptom questionnaires and cognitive function tests.

b. Procedure Risks

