Blood would be collected in the same sterile fashion as the patients' routine lab checks. Since the patients are on hemodialysis, blood will be collected in the same fashion as their routine monthly labs through the hemodialysis tubing. We will monitor levels of common blood chemistry such as serum potassium and CO₂ as well as monitor blood pressure and weights during the study. We will adjust the hemodialysis prescription and medications based on this monitoring. We will visit the patients weekly to monitor for any symptoms. Hemodialysis will be prescribed according to current National Kidney Foundation Committee guidelines to ensure adequate treatment for the patients.

c. Will it be possible to continue the more (most) appropriate therapy for the participant(s) after the conclusion of the study?

Yes

d. Study Endpoint(s)

The primary endpoint is quality of life as assessed by the KDQOL-36, a questionnaire designed to assess the symptoms commonly experienced with kidney disease. Other endpoints are an additional symptom questionnaire (Dialysis Symptom Index), cognitive testing (Trails Making B and Digit Symbol Substitution Test), and plasma levels of

uremic solutes. We are testing for equivalency between two approved ways of prescribing the hemodialysis. A Data Safety Monitor will review results regularly and report to us and the IRB on any departure from this expectation. If no unexpected differences are detected, the study will end once the projected total subject population has completed the study.

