Efficacy of Twice Weekly Hemodialysis in Patients With Residual Kidney Function

NCT03874117

April 30, 2025

Data Analysis Plans

The prespecified primary outcome is the quality of life assessed by the KDQOL-36. Secondary outcomes are symptom burden assessed by the Dialysis Symptom Index, cognition assessed by the Trails Making B Test and Digit Substitution Test, and plasma solute levels. Equivalence between twice weekly and thrice weekly hemodialysis will be assessed based on the KDQOL-36 score using a mixed-effects model with a random intercept to take into account the repeated measures per patient. Treatment-by-period effect will be first tested by adding a treatment-by-period interaction; if nonsignificant, the treatment effect will be estimated with period and treatment as the covariates, and if significant, the treatment effect will be estimated using a linear regression model with data from the first period only. A two-sided 90% confidence interval (CI) will be calculated and equivalence concluded if the CI is contained within the prespecified margin of -5 and 5 for the KDQOL-36 score. For analysis of other outcomes, we will compare means using a mixed-effects model and medians using quantile regression with robust standard errors to account for the multiple observations per patient. The mixed-effects model assumed data to be missing at random while quantile regression assumed data to be completely missing at random. All analysis assumed 5% significance.

Rationale for Sample Size

The power calculation was based on a previous study in which repeat measures of the KDQOL-36 score at six weeks in a group of control hemodialysis patients had a paired difference of 2.1 ± 5.7 compared to the original value. Based on this finding, 30 patients would provide more than 90% power to test whether twice weekly hemodialysis was equivalent to thrice weekly hemodialysis with the equivalence margin defined as -5 and 5. The equivalence margin (γ) was chosen based on previous studies showing no association with adverse outcomes with this degree of reduction.

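### Does the SAP need to name a period term in the models for the secondary outcomes?

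*SAP*

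**What the plan says.** The Protocol (section 2a, Procedures) describes a randomised cross-over: patients "will undergo two 4-week study periods in a cross-over design". At the end of each period "patients will complete symptom questionnaires and cognitive function tests". Anyone who completes the study therefore takes the cognitive tests at least twice.

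The SAP (Data Analysis Plans) describes the KDQOL-36 model in some detail. It has a random intercept per patient and a preliminary treatment-by-period test; then, "if nonsignificant, the treatment effect will be estimated with period and treatment as the covariates".

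The other outcomes are introduced as follows: "Secondary outcomes are symptom burden assessed by the Dialysis Symptom Index, cognition assessed by the Trails Making B Test and Digit Substitution Test", together with plasma solute levels. For these the SAP gives model types only. The analysts will "compare means using a mixed-effects model and medians using quantile regression with robust standard errors to account for the multiple observations per patient". It does not list covariates, and it does not say whether the period term of the primary model carries over. The sentence on missing data that follows speaks of the mixed-effects model in the singular, without separating primary from secondary use.

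**The concern.** A model with treatment alone would comply with the text for the secondary outcomes. In a two-period cross-over such a model leaves any shift between periods in the residual. Practice on a timed cognitive test is a plausible source of such a shift, and every patient repeats those tests.

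The possible consequences are wider reported intervals and lower power for symptoms, cognition and solutes, plus some bias if the two sequences end up unequal in size. The direction matters. These outcomes help to show whether fewer sessions do harm, and the equivalence margin is stated for the KDQOL-36 only. A conservative test makes a true difference easier to miss, and a non-significant result might be taken as reassurance.

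**Working it through.** **Inputs.** From the SAP: 30 patients, margin −5 to 5, KDQOL-36 paired difference 2.1 ± 5.7 in control patients over six weeks, 5% significance. Assumed, because the documents do not give them: equal sequences (15/15), and a period effect π (period 2 minus period 1) of 0.2, 0.37, 0.5 or 1.0 SD of the paired difference. The value 0.37 is 2.1/5.7. It comes from the primary outcome and only illustrates a plausible size.

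**The plan's own figure.** The SAP states more than 90% power for the KDQOL-36. The standard error is 5.7/√30 = 1.041. With two one-sided 5% tests and a true difference of zero, power = 2Φ(5/1.041 − 1.645) − 1 = 99.8%, which agrees with the statement. The SAP gives no such figure for a secondary outcome, so the rest is in units of the paired-difference SD.

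**Reported standard error.** For complete pairs, the treatment estimate from the random-intercept model is the mean within-patient difference. That difference has expectation τ + π in one sequence and τ − π in the other, where τ is the treatment effect. With period fitted, Var = 1/n on 28 df. Without it, the expected estimated variance is (1 + π²·n/(n−1))/n on 29 df. The ratio of reported standard errors is therefore √(1 + π²·n/(n−1)). At n = 30 and π = 0.5 this is √(1 + 0.25 × 30/29) = 1.122.

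| π (SD) | SE ratio, n = 30 | Type I error without period | Power at τ = 0.5 SD without period |
|---|---|---|---|
| 0.2 | 1.020 | 4.7% | 74% |
| 0.37 | 1.068 | 3.7% | 71% |
| 0.5 | 1.122 | 2.8% | 67% |
| 1.0 | 1.426 | 0.6% | 44% |

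Type I error and power are from simulation at a two-sided 5% level, 60,000 runs per setting. With period fitted, type I error is 4.9% to 5.1% and power is 75% (exactly 75.3% from the noncentral t with 28 df). At the Protocol's approximate enrolment of 50, the SE ratios are 1.020, 1.068, 1.120 and 1.421.

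**Actual precision.** With 15/15, +π and −π cancel in the mean. The true SD of the estimate is 1/√30 = 0.183 whatever π is, and simulation gave 0.182 at every π from 0 to 1. What rises is the average reported standard error, from 0.181 to 0.259 over the same range. The estimate loses nothing; its interval is too wide.

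**Bias with unequal sequences.** Bias = π(n₁ − n₂)/(n₁ + n₂). At 16/14 it is 2/30 = 6.7% of π, and at 16/12 it is 4/28 = 14%. For π = 0.5 these are 0.03 and 0.07 SD, against a standard error of 0.18 to 0.19. At 18/12 the bias is 20% of π, but simulated type I error stays near nominal (5.2% at π = 0.37). At 20/10 it is 33% of π, and type I error reaches 7.9% at π = 0.37 and 10.3% at π = 0.5.

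**Medians.** The residual-variance argument does not transfer directly to quantile regression. In a simulation of 1,500 trials with paired SD 5.7 and an assumed between-patient SD of 10, the SD of the estimate without and with period was 1.93 and 1.65 at no period effect (ratio 1.17), and 1.98 and 1.66 at a shift of 2.1 (ratio 1.19). Most of that gap is there without any period effect.

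**Cost of fitting period when there is no period effect.** The ratio of t critical values is 2.0484/2.0452 = 1.0016, so the interval widens by about 0.2%.

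**The case for a change.** The best case for a change is that a prespecified plan should not rely on implication, least of all when it spells out the period term for one outcome and is silent on the rest. Two analysts could follow this SAP and report different standard errors for the same test. One added sentence would settle it at a cost of one degree of freedom. The allocation ratio is not stated either, so some imbalance cannot be excluded.

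The silence is real, and so is the arithmetic. A sentence naming the covariates would be tidy. But the argument shows missing detail and does not identify a wrong method. It yields a loss only if the analysts fit period for the KDQOL-36 and then leave it out, without being told to, when they fit the same type of model to data from the same visits.

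The larger losses also need inputs that the documents do not supply. The 43% figure requires a period shift of a full paired-difference SD. Type I error clearly above nominal appeared only at a 20/10 split. Practice is a reason to expect a shift on the two cognitive tests, and it does not extend to plasma solutes.

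Whether the quantile-regression errors are clustered by patient is not a separate gap, since the SAP gives that as their purpose.

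**Conclusion.** No change to the plan is needed. The SAP leaves the covariates of the secondary models unnamed, and analysts who already model period for the primary outcome can be expected to fill that gap in the obvious way.

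Under the less natural reading, with equal sequences and complete pairs, the estimates stay unbiased and as precise as before. The tests are conservative, and reported standard errors are about 2% to 12% too large for assumed period effects of 0.2 to 0.5 SD. Power for an assumed 0.5 SD treatment effect falls from 75% to between 74% and 67%. Mild imbalance (16/14 or 16/12) adds a bias well below the standard error.

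All of this concerns secondary outcomes. The KDQOL-36 equivalence analysis, which names period, is not affected. The conclusion would weaken only if a large period effect, a markedly unequal split and a treatment-only fit occurred together, and the documents give no reason to expect that.

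### The SAP does not say whether means or medians decide the secondary outcomes, and the planned quantile regression uses the crossover pairing inefficiently

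*SAP*

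**What the plan says.** The Protocol (section 2a, Procedures) says that patients "will undergo two 4-week study periods in a cross-over design", with outcomes taken at the end of each period. Every completer therefore supplies a pair of values.

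The SAP (Data Analysis Plans) lists the secondary outcomes: "Secondary outcomes are symptom burden assessed by the Dialysis Symptom Index, cognition assessed by the Trails Making B Test and Digit Substitution Test", together with plasma solute levels. One sentence then plans two analyses. The first half reads "For analysis of other outcomes, we will compare means using a mixed-effects model". The second half adds "medians using quantile regression with robust standard errors to account for the multiple observations per patient". The level is set by "All analysis assumed 5% significance"; sidedness is not stated for these outcomes.

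The SAP does not say:
- whether both analyses are run on every outcome, or means on some and medians on others;
- which result decides if they differ;
- whether the quantile model contains patient effects or a period term.

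The equivalence margin and the sample-size rationale concern KDQOL-36 only.

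**The concern.** A crossover gets its precision from within-patient differences. A quantile regression whose only allowance for repeated measures is a robust standard error estimates the median across patients on twice weekly treatment minus the median across patients on thrice weekly treatment. The clustered error accounts for the correlation between those two medians, but the estimate is not built from within-patient differences, so much of the between-patient spread stays in it. The loss does not depend on missing data. The SAP's statement that "quantile regression assumed data to be completely missing at random" is a separate matter.

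Symptoms, cognition and solutes bear on whether less dialysis is acceptable, and none of them has an equivalence margin. A non-significant result from a low-power median test could be taken as reassurance. With no deciding analysis named, the reader cannot tell which of two possibly conflicting results is the finding.

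**Working it through.** **The plan's own figure.** The only stated power is for the primary outcome: "30 patients would provide more than 90% power to test whether twice weekly hemodialysis was equivalent to thrice weekly hemodialysis", from a previous study whose controls "had a paired difference of 2.1 ± 5.7 compared to the original value". With SE = 5.7/√30 = 1.041, margin ±5 and two one-sided 5% tests:
- true difference 0: 2Φ(5/1.041 − 1.645) − 1 = 99.8%;
- true difference 2.1: Φ(2.9/1.041 − 1.645) = 87.3%.

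The stated power reproduces when the true difference is near zero. The dependence on 2.1 is a separate issue. No figure exists for any secondary outcome, so what follows rests on assumptions.

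**Inputs.** n = 30 (SAP). Assumed: complete data, bivariate normal log values with common SD s, within-patient correlation ρ from 0.5 to 0.9, two-sided 5% tests. A median is carried through a log transform unchanged, so the median contrast can be judged on the log scale.

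**Large-sample variances.**
- Paired mean difference of logs: 2s²(1 − ρ)/n
- Difference of marginal medians, correlation kept: 2s²(π/2 − arcsin ρ)/n = 2s²·arccos(ρ)/n
- Median of within-patient differences: (π/2)·2s²(1 − ρ)/n

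The variance ratio against the paired log mean is arccos(ρ)/(1 − ρ), and 30 divided by this is the effective number of patients. Against the median of differences, multiply that number by π/2.

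| ρ | Variance ratio | Worth, vs paired log mean | Worth, vs median of differences |
|---|---|---|---|
| 0.5 | 2.09 | 14.3 | 22.5 |
| 0.7 | 2.65 | 11.3 | 17.8 |
| 0.8 | 3.22 | 9.3 | 14.6 |
| 0.9 | 4.51 | 6.7 | 10.4 |

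Simulation at n = 30 with normal data is slightly kinder: 15.1, 12.7 and 7.7 at ρ = 0.5, 0.7 and 0.9 against the paired mean.

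**How much of the loss is lost pairing.** Pairing cuts the variance of a mean contrast by ρ and that of the marginal-median contrast by (2/π)·arcsin ρ: 33%, 49%, 59% and 71% at the four correlations. The share of the reduction kept is therefore 67%, 71%, 74% and 79%. At ρ = 0 a median is already worth only 30 × 2/π = 19.1. At ρ = 0.5 the total fall is 30 − 14.3 = 15.7 patients, of which 30 − 19.1 = 10.9 is the ordinary cost of a median and 4.8 is pairing. At ρ = 0.9 the fall is 23.3, of which 10.9 is the median and 12.4 is pairing.

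**Power in one scenario.** Log SD 0.6, ρ = 0.8, values 25% higher on one schedule: ln 1.25 = 0.223.
- Paired log analysis: SE = 0.6 × √(0.4/30) = 0.0693; Φ(0.223/0.0693 − 1.96) = 90%.
- Marginal medians: SE = 0.0693 × √3.22 = 0.124; Φ(0.223/0.124 − 1.96) = 43–44%.

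These are large-sample values. Simulation at n = 30 gives 36% to 40% for the median regression, depending on how the clustered error is computed, 77% for the raw-scale mean model, 82% for the signed-rank test and 87% to 88% for the log-scale model.

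**Sensitivity.** At ρ = 0.5, same SD and effect, simulated power is 25% (median), 39% (raw mean) and 48% (log). Mean and median tests disagree at 5% in 30% of those trials, against 47% to 52% in scenarios with ρ = 0.8. With no true difference, at least one of the two is significant in 6% to 9% of trials.

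**The case against.** The strongest reply is that the SAP also plans a mixed model for means, which uses the pairing. A reader might infer from the quantile-regression clause alone that secondary outcomes are compared only on medians and that real differences will be reported as none. The documents do not support that. If both tests are run, at least one is significant in about 82% of trials in the scenario above, against 88% for a log-scale model. The 40% applies only where the median test alone decides, which the SAP neither states nor rules out. Nor does it say that a non-significant median test will be reported as no difference.

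It is also tempting to say that the quantile regression throws away most of the pairing. In variance terms it does not: two thirds to four fifths of the reduction is kept, and at ρ = 0.5 most of the fall from 30 is the usual price of a median.

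Three further points have weight. The log-scale comparator is the best available method for exactly log-normal data, so 14 to 7 is the less favourable comparison for the median; 22 to 10 compares one median-based method with another. Every magnitude depends on an assumed correlation, and at ρ = 0.3 the worth is 16.6. Reporting medians for skewed outcomes is a legitimate choice of what to estimate.

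What remains is that the deciding analysis is unnamed and that, wherever medians decide, a within-patient method is more precise at every correlation in that range. Skewed outcomes are where an analyst is most likely to turn to the median. There the raw-scale mean model is also inefficient (77% against 87%), so falling back on it is not a full answer.

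**Conclusion.** The concern holds in a limited form. The SAP leaves open which of two analyses decides each secondary outcome. One of them, on its natural reading as a marginal model without patient effects, uses the crossover data inefficiently even when nothing is missing. The size ranges given rest on log-normality and on correlations of 0.5 to 0.9, neither of which the documents supply; the direction does not depend on the exact correlation. The consequence is a greater chance of missing moderate differences on outcomes judged by the median. It is not a certainty of missing them, nor a failure of the secondary analysis as a whole. False positives from running two tests are a minor matter. This is a worthwhile, inexpensive improvement to the secondary analyses.

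**What to change.** Drop the quantile regression as an inferential analysis and name one deciding analysis per secondary outcome:

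- **Plasma solutes and Trails B time (expected to be right-skewed):** mixed model on log values with a random patient intercept, treatment and period; report the ratio of geometric means with a 95% CI.
- **Dialysis Symptom Index and digit symbol score:** the same model on the raw scale; report the mean difference with a 95% CI.
- **If a distribution-free result is wanted:** a period-adjusted Hodges-Lehmann estimate from within-patient differences, that is, the median of their pairwise averages.
- **Group medians:** descriptive only.

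This takes a few sentences in the SAP and uses data that the trial collects anyway. There are three costs. Results for skewed outcomes become ratios. The geometric-mean ratio equals the ratio of medians only if log values are symmetric, which should be stated. Undetectable solute values need a floor set in advance.
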